Regarding complement, African-Americans have been shown to have increased C4 levels⁶⁸, differences in C4 gene copy number in relationship to lupus⁶⁹⁻⁷², and different C3 polymorphism frequencies⁷³ than Caucasians. Regarding the latter have higher C3s allele frequency compared to Caucasians (93 versus 83%).⁷³ [name] studied the relationships between complement and obesity in 189 African American (Black) and 331 Caucasian (White) adult subjects from central Ohio.^{74,75} Between race differences in C3 and C4 levels were noted with increased BMI and C4 levels and decreased C3 levels in African-Americans. In each race group, strong correlations were seen between C3 and C4 protein concentrations, C4 protein levels and gene copy number of C4, BMI and C3 concentrations, BMI and C4 concentrations, and BMI and yield of C4 protein per copy of gene. In an earlier study of Hungarian subjects, positive correlations between serum C3 levels and total cholesterol concentration and between C3 levels and triglyceride levels were seen.⁴⁴

Significance: There are three important areas of innovation in the proposed studies.

1. ***Our study will be the first to explore the relationships of C3 and C4 levels to cardiovascular risk factors in African-Americans.*** This is important follow-up to our current study of nonHispanic Caucasian adolescents (Data presented below) because of the demonstrated differences in cardiovascular disease between African-American and Caucasian adults and in cardiovascular risk in adolescents. These studies will help us determine potential mechanisms for these differences early in the course of the disease.
2. ***Our study will be the first to explore the relationship between C3 polymorphisms and traditional and non-traditional anthropometric, biochemical, and functional cardiometabolic risk factors in African American adolescents.*** No studies have been done examining the role of C3 polymorphisms on cardiometabolic risk in adult or adolescent African-Americans. Again because of the increased cardiovascular disease and risk and because of the different polymorphism frequency in African-Americans it is clearly important that this population be studied.

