Increased C4S copy number was associated with increased insulin secretion ($\beta=0.29$; CI: 0.06-0.52) and decreased endothelin 1 ($\beta=-0.15$; CI: -0.30--0.01). WBC ($\beta=-0.79$; CI: -1.56--0.02) and neutrophil count ($\beta=-0.87$; CI: -1.48--0.33) both decreased with increasing C4B copy number.

Figure 2: Relationship of HDL to C4 type copy number. C4L: $\beta=3.59$; CI: 1.19-6.00; C4S: $\beta=0.4.26$; CI: -7.50—1.02; C4A: $\beta=4.33$; CI: 1.00-7.66; C4B $\beta=-5.56$; CI: -10.3--0.87.

Interestingly, the measures of inflammation, IL6 and CRP were not related to C4 copy number nor were AIX₇₅ or PAI-1.

RESEARCH DESIGN AND METHODS

All three specific aims will be studied using the same subjects and research procedures.

Subjects: One hundred Africa-American adolescents between the ages of 12 and 18 will be recruited to participate. There will be no weight or BMI criteria and we plan to recruit subjects across a wide range of BMI's. This will allow us to determine the role of C3 and C4 levels, C3 polymorphisms and C4 copy number variation in determining adolescent obesity and cardiometabolic risk. Subjects must be on no chronic medications except for contraceptives in females. Subjects will be expected to be medication free for at least 2 weeks prior to study except for contraceptives. Subjects with a history of autoimmune disease, either endocrine or connective tissue type will be excluded. Subjects with a history of hematologic or renal disease, malignancy or other chronic disease will also be excluded. Subjects with a history of asthma or attention deficit disorder will be allowed to participate as long as they meet the medication requirements.

To avoid potential racial confounders as described in the preliminary data, we plan to recruit only African-American subjects. Subjects will be recruited to specifically fill 3 different weight classes (70 % lean, BMI <85%: 10% overweight BMI<95%: 20% obese BMI>95%) for both sexes. These match the reported US prevalences for overweight and obesity.⁷⁶

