Sample size: Based on data from our previous study with 100 nonHispanic white subjects and 100 African-American subjects we have power 0.8 to detect a 15% racial difference in C4 levels and 7.5% difference in C3 levels.

Interpretation: There are two major portions of this aim. The first is to determine whether there are complement levels differences between the racial groups and the second is to determine how these affect previously demonstrated racial differences in cardiovascular risk¹². The former will be easily determined by comparing complement levels in the two groups. The hypothesis that these racial differences are responsible for at least some of the cardiometabolic racial differences will be proven if when complement levels are included in the regression equation they retain significance but the racial differences are lost. Lastly, even if racial differences in complement are not found or do not account for cardiometabolic risk differences it will still be important for us to determine whether the significant effects of complement described above in nonHispanic whites are present in African-American adolescents.

Specific Aim 2: To determine whether specific C3 polymorphisms, F versus S, A>G at rs11569562 and/or rs2250656, are associated with increased cardiometabolic risk in African-Americans.

Statistical Methods: As indicated above, the C3F gene has been associated with increased risk of myocardial infarction in several populations³⁶⁻³⁸ and Phillips et al⁴⁰ reported increased cardiometabolic risk in subjects with either an A/A or A/G versus subjects with a G/G genotype for both the rs11569562 and the rs2250656 sites. For rs11569562 in a European population ~ 25% of subjects had G/G and for rs2250656 ~10% had G/G. Frequencies in the African-American population are unknown. Data will be assessed for normality using the Shapiro Wilk test ($p>0.05$ indicative of normality). Non normal data will be log normalized if possible. Unpaired t-tests with unequal sample sizes will be used for comparisons for each of the measured normal variables between subjects with at least one A allele gene and those with two G alleles assuming the data is normally distributed. Mann-Whitney U tests will be used to assess non-normal data.

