Sample size: Based on our preliminary data for the F versus polymorphism and the data of Philips et al⁴⁰ site we will be able to effect size variable differences of 0.47 for the F versus S polymorphism, 0.7 for rs11569562 and 1 for rs2250656 with $\alpha=0.05$ and $\beta=0.8$ within African-Americans.

Interpretation: Our hypothesis will be proven by increased BMI, waist circumference, percent body fat, blood pressure, triglycerides, LDL cholesterol, CRP, IL-6, fibrinogen, and/or PAI-1 and/or decreased HDL, insulin sensitivity, disposition index, or reactive hyperemic responses in subjects with at least one F or one A allele and/or if the subjects with at least one allele have increased worsening over 1 year than do those without. Previous studies of the effects of complement on cardiometabolic risk in adults have found differences in some risk factors but not others although there is disagreement on the areas affected.^{11,18,20}

Specific Aim 3: To determine whether C4 gene copy number variation is associated with increased cardiometabolic risk in African-American adolescents.

Statistical methods: Robust rank order regression will be used to assess the relationship of C4 gene copy number for each C4 subtype and cardiometabolic risk. Age and sex will be included in all models.

Sample size: With 99 subjects we will be able to detect an $r=0.28$ with $\alpha=0.05$ and $\beta=0.80$ for each analysis without correction for multiple analyses. There is no literature available to assess whether an $r=0.28$ is a reasonable expectation but r -values below this are unlikely to indicate important mechanistic relationships.

Interpretation: Our hypothesis will be proven by positive relationships between C4 copy number and BMI, waist circumference, percent body fat, blood pressure, triglycerides, LDL cholesterol, CRP, IL-6, fibrinogen, and/or PAI-1 and/or negative relationships to HDL, insulin sensitivity, disposition index or reactive hyperemic responses. The main limitation of this study is sample size. No studies have been done to identify expected effect sizes for these variables in African Americans. As indicated for rs11569562 we will be able to detect differences with an effect size of 0.7 and for rs2250656 with an effect size of 1. Smaller differences with physiological significance could be present but may not be statistically significant in this population.

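### Aim 2 compares genotype groups without age and sex, unlike Aim 3 and the Aim 1 regressions, and leaves the t-test form unstated; an adjusted model with robust errors is a cheap, conditional gain.

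*Combined protocol and SAP*

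**What the plan says.** All references are to the Combined protocol and SAP.

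- **Data analysis, Specific Aim 2, Statistical Methods.** After a Shapiro-Wilk check and a log transform where possible: "Unpaired t-tests with unequal sample sizes will be used for comparisons for each of the measured normal variables". The contrast is carriers of at least one A allele against G/G. For the rest, "Mann-Whitney U tests will be used to assess non-normal data". No covariate and no unequal-variance form is mentioned.
- **Expected group sizes, same section.** "For rs11569562 in a European population ~ 25% of subjects had G/G and for rs2250656 ~10% had G/G". It adds: "Frequencies in the African-American population are unknown".
- **Specific Aim 3, Statistical methods.** Robust rank regression of the risk factors on C4 copy number: "Age and sex will be included in all models". The same sentence follows the regression description in Specific Aim 1.
- **Specific Aim 1, race comparison.** This is also an unpaired t-test. Analysis of covariance follows only if the races differ in age or BMI; sex is not named.
- **Research Design and Methods, Subjects.** "One hundred Africa-American adolescents between the ages of 12 and 18 will be recruited to participate", of both sexes.

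**The concern.** Aims 2 and 3 ask parallel questions of the same subjects and much the same outcomes: does C3 genotype, or C4 copy number, relate to cardiometabolic risk? One is adjusted for age and sex and the other is not, and no reason is given. Outcomes such as waist circumference, percent body fat, blood pressure and HDL can plausibly vary with age and sex between 12 and 18. Where they do, leaving both out keeps avoidable variance in the comparison.

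The second matter is the form of the test. Stating that sample sizes are unequal does not say whether unequal variances are allowed for. With expected splits near 25:75 and 10:90, the pooled t-test's error rate is sensitive to a difference in SD between the groups, and Welch's is not. At stake are some power in comparisons that the plan itself calls limited by sample size, and the trustworthiness of the p-values if spreads differ.

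**Working it through.** **Inputs from the documents.** N = 100; G/G about 25% (rs11569562) and 10% (rs2250656), both European figures; alpha 0.05; power 0.8; stated detectable effects 0.7 and 1. **Assumed.** Two-sided testing; the share R² of outcome variance explained by age and sex, 0 to 0.30; the ratio of the small group's SD to the large group's, 0.67 to 2.

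**1. The plan's own figures.** For a two-sample t-test, power = P(T > 1.984), where T is noncentral t with 98 df and noncentrality d/√(1/n₁+1/n₂).

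- 25:75: √(1/25+1/75) = 0.2309. Power of 80% needs d = 0.653. At the stated 0.7, power is 85.1%.
- 10:90: √(1/10+1/90) = 0.3333. Power of 80% needs d = 0.943. At the stated 1, power is 84.4%.

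Both detectable effects round to the stated values, so these figures fit an unadjusted two-sided t-test. The stated 0.47 for F versus S does not reproduce with 100 subjects (even 50:50 gives 0.566). That is a separate matter and is not used here.

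**2. Gain from adjustment, ordinary errors.** The residual SD is multiplied by √(1−R²), and so is the detectable effect. Power is taken at d = 0.653 or 0.943.

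| R² | √(1−R²) | Detectable, 25:75 | Detectable, 10:90 | Power |
|---|---|---|---|---|
| 0 | 1 | 0.653 | 0.943 | 80% |
| 0.05 | 0.975 | 0.637 | 0.919 | 82% |
| 0.10 | 0.949 | 0.620 | 0.895 | 84% |
| 0.20 | 0.894 | 0.584 | 0.844 | 88% |
| 0.30 | 0.837 | 0.547 | 0.789 | 92% |

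**3. Pooled t-test with unequal spread.** Take the small group's SD as k times the large group's. At 10:90 and k = 1.5:

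- true variance of the difference = 2.25/10 + 1/90 = 0.236;
- pooled variance ≈ (9×2.25 + 89)/98 = 1.115, so the test uses 1.115 × 0.1111 = 0.124;
- the standard error is too small by √(0.236/0.124) = 1.38, so the effective cut-off is 1.984/1.38 = 1.44, a two-sided error of about 15%.

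Simulation (40,000 data sets per case) agrees:

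| SD ratio k | Pooled, 10:90 | Pooled, 25:75 |
|---|---|---|
| 0.67 | 0.8% | 1.8% |
| 1 | 5.0% | 4.9% |
| 1.5 | 15.3% | 10.5% |
| 2 | 24.6% | 15.5% |

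Welch stays near 5% in every case.

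**4. What the remedy delivers.** In simulation at 10:90, a linear model with genotype, age and sex and HC3 errors had type I error of about 5% to 7% across these SD ratios. The same model with ordinary errors ranged from 0.8% to about 23%, so adjustment alone does not cure unequal spread. HC3 has a price. With equal variances and d = 0.943, its power at 10:90 was:

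| R² | HC3 | Ordinary errors |
|---|---|---|
| 0 | 75% | 80% |
| 0.10 | 80% | 84% |
| 0.20 | 83% | 88% |
| 0.30 | 88% | 92% |

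At 25:75 (d = 0.653) HC3 gave 78%, 80%, 82% and 90% at R² of 0, 0.05, 0.10 and 0.30. Unadjusted Welch at 10:90 with equal variances has about 73% power.

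**The case against.** The strongest reply is that nothing here is shown to be wrong, and most of it stands.

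- **Contrast with Aim 1.** A reader might infer that every other analysis is adjusted. It is not: the sentence on age and sex in Aim 1 belongs to its regressions, and its race comparison is itself a t-test. The clean contrast is with Aim 3 and the Aim 1 regressions.
- **Confounding.** A reader might infer bias from imbalance. With 10 against 90, the chance difference in the proportion female does have an SD of √(0.25×(1/10+1/90)) = 0.167, or 17 points. But this is random variation that the standard error already covers. The Background places C3 on chromosome 19, an autosome, so no systematic link with sex is expected, and none with age.
- **Unequal group sizes.** These alone do not invalidate a t-test. Harm needs unequal SDs and the pooled form; the documents state neither, and the planned log transform may reduce differences in spread.
- **Power ranking.** A reader might infer that Aim 2 is the weakest aim. As point-biserial correlations, r = d/√(d² + 1/(pq)), where p is the G/G share and q = 1−p: 0.653 at 25:75 and 0.943 at 10:90 both give 0.27, against the r = 0.28 stated for Aim 3. The two are alike.
- **R² is undocumented.** The null age and sex results under Preliminary Studies concern complement levels, not the Aim 2 outcomes. At R² of 0.05 to 0.20 the detectable effect falls only about 2.5% to 10.5%.

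What remains is that Aim 2 omits two available covariates used in its sister aim and leaves open a test choice that can alter the error rate. Mann-Whitney supplies neither adjustment nor protection against unequal spread.

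**Conclusion.** The point holds as one of precision, consistency and an unstated test form. It does not show that Aim 2 is biased or invalid.

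The precision gain rests wholly on an assumed R². It is nil near zero, and with ordinary errors the detectable effect falls by about 5% to 16% for R² of 0.10 to 0.30 (1−√0.9 and 1−√0.7). The type I error of about 15% to 25% at 10:90 is conditional on a pooled test and on a small-group SD 1.5 to 2 times larger; nothing in the documents says that either applies. The splits are European, so the actual imbalance may be milder or more extreme.

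With HC3 errors at 10:90, the net power gain over the planned t-test appears only above an R² of about 0.10. Below that, the benefit is a protected error rate and consistency with Aim 3, paid for with a few points of power.

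**What to change.** In Specific Aim 2, Statistical Methods, replace the two-group tests with a linear model for each outcome, log-transformed where needed, on the genotype indicator plus age and sex, with HC3 standard errors.

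If a two-group test is kept, name Welch, and note that at 10:90 with equal variances its power is about 73% rather than 80%.

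The robust rank regression of Aims 1 and 3 would restore consistency on covariates, but should not be offered as protection against unequal variances. A proxy, least squares on ranks at 10:90, gave type I errors of 9.9% and 11.8% at SD ratios of 1.5 and 2, and 1.9% at 0.67. The planned procedure may differ, but nothing shows that it does better.

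**Cost:** a cheap improvement. It needs a change of wording and no new data, since the plan already uses age and sex in its other models. The statistical price is about 3 to 5 points of power for HC3 against ordinary errors at 10:90, and the plan should say so.

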Complement genetics: The C3 gene is on the short arm of chromosome 19 and several polymorphisms have been described. There are two major phenotypic variants of C3 proteins: the F-variant that travels faster and the S-variant that travels slower in an immunofixation gel based on electric charge difference of these two protein molecules. The molecular basis for such Fast to Slow (F vs S) phenotypic variation is due to a C>G DNA polymorphism that leads to glycine to arginine change at amino acid residue 102 (G102R).³⁵ The C3F polymorphism has been associated with myocardial infarction^{36,37} and atherosclerosis³⁸ in several, but not all studies.³⁹ Phillips et al⁴⁰ found that patients with metabolic syndrome had specific polymorphisms present at the following locations rs11569562, rs2250656, rs1047286, and rs2230199. Multivariate modeling revealed that only the first two were significant. Interesting both are in the intron of the C3 gene and for both the A/A and A/G genotypes are associated with increased C3 production.^{40,41} Regarding phenotype subjects with A/A or A/G alleles at rs11596562 had higher triglyceride, insulin, and c-peptide and lower HDL than subjects with two G alleles. For the rs2250656 polymorphism subjects with A/A or A/G had increased BMI, abdominal obesity, and lower HDL and insulin sensitivity compared to those with G/G.

The C4 gene is located on chromosome 6 and there is significant copy number variation. Low copy number is associated with decreased serum C4 levels⁴²⁻⁴⁴ and increased risk of autoimmune disease including lupus, rheumatoid arthritis, and possibly type 1 diabetes.⁴⁵⁻⁴⁸ Associations between C4 gene copy number variation and cardiovascular risk have not been investigated in depth but C4 gene copy number has been associated with longevity. Different forms of C4 [acidic (C4A), basic (C4B), long (C4L) and short (C4S)] also exist and there is copy number variation for each. Low C4B gene copy number has been shown to be associated with increased cardiovascular risk in several studies⁴⁹⁻⁵⁴ and decreased longevity in Hungarian subjects^{55,56} and Icelandic smokers⁴⁹ while decreased C4L gene copy number is associated with increased longevity in Germans⁵⁷.

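### Aims 2 and 3 count as proven on any one of 14 outcomes with no multiplicity control, so chance alone would often deliver the verdict

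*Combined protocol and SAP*

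**What the plan says.** **Aim 2, Interpretation.** The rule is: "Our hypothesis will be proven by increased BMI, waist circumference, percent body fat, blood pressure, triglycerides, LDL cholesterol, CRP, IL-6, fibrinogen, and/or PAI-1". It continues, again with and/or, to lower HDL, insulin sensitivity, disposition index or reactive hyperemia in carriers of at least one F or one A allele. That makes 10 outcomes that count if raised and 4 that count if lowered. A further route follows: "and/or if the subjects with at least one allele have increased worsening over 1 year than do those without".

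**Aim 3, Interpretation.** "Our hypothesis will be proven by positive relationships between C4 copy number and BMI" opens the same list of 14, with the same four outcomes counting in the negative direction. The Aim 3 methods run the regression separately for each C4 subtype. The section on complement genotypes measures C4A, C4B, long and short genes, and total C4.

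**Multiplicity.** It is mentioned once, in the Aim 3 sample-size statement, where the detectable correlation holds "for each analysis without correction for multiple analyses". Neither Interpretation paragraph gives a p-value threshold, a primary outcome, an order of testing or a minimum number of positive results.

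**Tone elsewhere.** The Specific Aims page describes the short-term objective as exploratory. Future Directions cautions that cross-sectional work does not establish causation. It also names the identification of high-risk subjects from complement genetics as the most immediate use of the results.

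**The concern.** A rule satisfied by any one of several dozen tests is easy to satisfy when nothing is going on. A verdict of proof reached that way says little about whether C3 or C4 genetics bear on cardiometabolic risk. No treatment decision hangs on it, but the plan points towards genetic identification of at-risk adolescents, where an over-read chance finding could do harm.

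The plan's own preliminary data show how the rule behaves. In the white cohort the only significant C3 genotype difference was lower HDL in F carriers (p=0.028). Under the Aim 2 rule, one such result would settle the hypothesis. Under Benjamini-Hochberg across just the 14 listed outcomes for one variant, an isolated result would need p ≤ 0.05/14 = 0.0036.

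Two smaller defects sit in the same paragraphs. The one-year route needs follow-up data that the protocol does not collect. The Aim 3 rule credits only higher copy number with higher risk, although the documents' evidence on direction is mixed.

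**Working it through.** **1. Which alpha is meant.** The plan states 99 subjects for r=0.28, alpha 0.05, power 0.80. By Fisher z, n = ((z₁₋α⁄₂ + z_power)/atanh r)² + 3.
- Two-sided: ((1.960 + 0.842)/0.2877)² + 3 = 97.8, so 98. This agrees with the stated 99, where power is 0.805.
- One-sided: 78, which does not agree.

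The plan's alpha therefore behaves as two-sided. A null test reaches two-sided p<0.05 in the adverse direction with probability 0.025.

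**2. Number of tests.** Outcomes: 10 + 4 = 14. Aim 2: 3 × 14 = 42. Aim 3: 4 × 14 = 56, or 5 × 14 = 70 with total C4.

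**3. Independent tests.** P(at least one) = 1 − 0.975^k:
- k=14: 29.8%
- k=42: 65.5%
- k=56: 75.8%
- k=70: 83.0%

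**4. Correlated tests.** The outcomes overlap and so do the predictors; of the two SNPs the Background says "both are in the intron of the C3 gene". The documents give no correlations, so all of those below are assumptions. Null test statistics were simulated with correlation (between predictors) × (between outcomes), oriented so that positive is adverse. A study counted as proven if any statistic exceeded 1.96.

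The more plausible outcome structure has BMI, waist and percent fat correlated 0.85 and every other pair 0.25.
- Aim 2: about 53%, 45% and 37% with between-variant correlation 0, 0.5 and 0.8.
- Aim 3: about 50–68%, depending on how closely gene length follows C4 type and on whether total C4 is counted.

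With one common correlation among all outcomes:

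| Setting | 0 | 0.3 | 0.5 | 0.7 |
|---|---|---|---|---|
| Aim 2, variants uncorrelated | 65% | 53% | 43% | 33% |
| Aim 2, variants correlated 0.5 | 60% | 45% | 36% | 27% |
| Aim 2, variants correlated 0.8 | 50% | 37% | 29% | 21% |
| Aim 3, length independent of type | 74–80% | 64–67% | 55–58% | 41–44% |
| Aim 3, partly linked | 68–75% | 59–63% | 50–54% | 36–41% |
| Aim 3, 97% linked | 59–70% | 54–61% | 44–50% | 31–37% |
| One variant alone, 14 outcomes | 30% | 22% | 17% | 12% |

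The Aim 3 rows respect the plan's identity that total C4 equals C4A + C4B and also long + short. They assume:
- 1/2/3 genes per haplotype with probability 0.20/0.65/0.15 (0.10/0.80/0.10 in the 97% row);
- C4A probability 0.55;
- long-gene probability 0.6 for both types; 0.9 (C4A) and 0.2 (C4B) for partly linked; 0.97 and 0.03 for 97% linked.

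Age and sex were not modelled. A repeat simulation agreed to within about two percentage points.

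**5. After correction.** Under the same nulls, Benjamini-Hochberg at 0.05 within an aim gives at least one finding in about 2–5% of studies counting either direction, and about 1–3% counting only the adverse direction.

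**6. One-year route.** The protocol describes one Study Visit, and Future Directions treats the design as cross-sectional. No second measurement exists from which worsening could be computed.

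**7. Direction in Aim 3.** In line with the rule: HDL fell as C4S and C4B rose; higher C4L went with impaired endothelial function and lower disposition index; decreased C4L was linked to longevity. Against it: HDL rose with C4A and C4L, and the Background links low C4B copy number to cardiovascular risk.

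**The case against.** The strongest reply is that this is an observational study that calls itself exploratory, admits that its Aim 3 power is uncorrected, names sample size as its main limitation and cautions against causal reading. That bears on weight, but it does not alter the two rules. The caution concerns causation, not chance, and exploratory aims do not need a verdict of proof.

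It is also fair that the rates belong to a rule completed by inference. The threshold is not stated. That any single variant suffices is explicit for Aim 2 only: the Aim 3 rule speaks of C4 copy number in general, and the any-subtype reading comes from the methods text. If one copy-number measure were meant, the single-variant row applies (12–30%).

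A reader might take 65% and 80% as the size of the problem. Those figures need 14 mutually uncorrelated outcomes, and the documents speak against that: many risk factors were related to body habitus in the preliminary data, and disposition index is computed from insulin sensitivity.

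Nor are the low ends floors. At outcome correlation 0.9 the rates are about 13–20% for Aim 2 and, under the looser copy-number structures, 22–28% for Aim 3. The lowest Aim 2 figures need between-variant correlation 0.8. With 13.5% F carriers (1 − 0.93², from the quoted S-allele frequency) and the European 75% and 90% A carriers, pairwise correlation cannot exceed 0.13–0.58. For the two SNPs, however, the plan says "Frequencies in the African-American population are unknown", so 0.8 cannot be ruled out.

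**Conclusion.** The point stands as a defect in the stated decision rules. Under the block correlation assumption, and counting one adverse-direction two-sided p<0.05, a study with no true association would be called proven in about 37–53% of cases for Aim 2 and 50–68% for Aim 3. Across wider assumed correlations the ranges are about 20–65% and 30–80%. Confidence is high that the rules are too permissive and low in any single percentage, since every correlation is assumed. Even one variant alone far exceeds the 2.5% of a single adverse-direction test.

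Two stronger readings are not supported. The one-year criterion does not raise the false-positive rate, because it cannot be evaluated; it is a wording error. And the documents do not make a formal correction obligatory: for aims labelled exploratory, dropping the verdict is enough.

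**What to change.** 1. Remove the statements that the hypotheses will be proven. Label Aims 2 and 3 exploratory, and report every estimate with its 95% CI together with the number of tests in each aim. This is a wording change with no cost in power, data or subjects.

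   If an aim-level claim is wanted, base it only on associations with Benjamini-Hochberg q<0.05 across that aim's pre-listed tests (42 for Aim 2; 56, or 70 with total C4, for Aim 3), and report the rest as exploratory. The cost is power for an isolated association. Bonferroni gives the worst case: in Aim 3, power at r=0.28 with 99 subjects falls from 80% to 29–31%, and the detectable r rises from 0.28 to 0.40–0.41. In Aim 2, power falls from 85% to 39% at effect size 0.7 (75/25 split) and from 84% to 37% at 1.0 (90/10 split).

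2. Delete the one-year worsening criterion.

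3. Only together with item 1, report C4 associations in either direction with their sign. Without item 1 this would widen the rule: counting either direction uncorrected gives 43–95% in Aim 3 across the assumed settings.
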